Patients with bilateral adrenal incidentalomas have recently been recognized to have a high incidence of subclinical hypercortisolism. Pasternak and colleagues noted that of 23 patients with bilateral adrenal incidentalomas, 21.7% of these patients had subclinical hypercortisolism, indicating a high prevalence in this subset of patients (34). Papierska and colleagues assessed patients with subclinical hypercortisolism and bilateral adrenal incidentalomas. In this study, 25 patients with bilateral adrenal tumors and subclinical hypercortisolism underwent a unilateral adrenalectomy of the larger of the two glands. In all surgical patients hypercortisolism was resolved. Fifty-eight percent of patients had clinical improvement of their diabetes, hypertension, and obesity. This study indicates that patients with bilateral adrenal incidentalomas and subclinical hypercortisolism can be treated by removing the larger of the two adrenal masses with a unilateral adrenalectomy (35)

2 ELIGIBILITY ASSESSMENT AND ENROLLMENT

2.1 ELIGIBILITY CRITERIA

2.1.1 Inclusion Criteria

- 2.1.1.1 An individual with an adrenal neoplasm less than 5 cm in size with biochemically confirmed evidence of hypercortisolism (2 out of 3: DST >3 mcg/dL, elevated urine

Abbreviated Title: Subclinical Hypercortisolism**Version Date: 12/19/2016**

free cortisol, and/or morning ACTH <2.2 pmol/l) without overt clinical signs and symptoms.

- 2.1.1.2 Age greater than or equal to 18 years.
 - 2.1.1.3 Adults must be able to understand and sign the informed consent document.
 - 2.1.1.4 Patients must have laboratory and physical examination parameters within acceptable limits by standard of practice guidelines prior to surgery as assessed by preoperative anesthesia assessment.
- 2.1.2 Exclusion Criteria
- 2.1.2.1 Biochemically and/or radiologically confirmed pheochromocytoma, hyperaldosteronoma, or adrenocortical carcinoma.
 - 2.1.2.2 Nonfunctioning adrenal neoplasm.
 - 2.1.2.3 Pre-existing cancers and/or metastatic disease to the adrenal glands.
 - 2.1.2.4 Pregnancy and/or lactation.
 - 2.1.2.5 Lack of metabolic complications.
 - 2.1.2.6 Imaging features worrisome for malignancy (heterogeneous tumor, presence of calcifications, necrosis, >10 Hounsfield units on an unenhanced CT scan, and delayed washout of contrast).

2.1.3 Recruitment Strategies

Since the NIH has an excellent medical endocrinology service with a large number of referrals and investigators across two institutes (NIDDK and NICHD), we are collaborating with our endocrine colleagues (who are also co-investigators in the protocol) to increase accrual to obtain the necessary number of patients. We will also provide information regarding our protocol at national and international meetings.

2.2 SCREENING EVALUATION

Patients will undergo the following screening evaluations which may be performed within 4 weeks of enrollment

2.2.1 Detailed History and Physical Examination

H&P will include vital signs, BMI, weight, waist circumference, ECOG status, demographic information and family history.

2.2.2 Radiology and Nuclear Medicine Tests

- 2.2.2.1 Adrenal protocol CT scan with and without intravenous contrast.

2.2.3 Laboratory evaluation

- 2.2.3.1 CBC with differential
- 2.2.3.2 Chemistry Panel [Sodium (Na), Potassium (K), Chloride (Cl), Total CO₂ (bicarbonate), Creatinine, Glucose, Urea Nitrogen (BUN), Albumin, Calcium total, Magnesium total (Mg), Inorganic Phosphorous, Alkaline Phosphatase, ALT/GPT, AST/GOT, Total Bilirubin, Direct Bilirubin, LD, Total Protein, Total CK, Uric Acid]

Abbreviated Title: Subclinical Hypercortisolism**Version Date: 12/19/2016****2.2.3.3 PT/PTT****2.2.4 Biochemical testing**

2.2.4.1 Fasting morning upright serum renin and plasma aldosterone levels

2.2.4.2 24 hour urinary free cortisol level

2.2.4.3 Midnight serum and salivary cortisol level

2.2.4.4 Baseline serum cortisol at 08:00 and 16:00 hours

2.2.4.5 Morning plasma ACTH at 08:00

2.2.4.6 Low dose dexamethasone suppression test

1mg overnight test with a cortisol suppression threshold set at 3 µg/dL

- cortisol at 08:00 hours
- plasma dexamethasone level at 08:00 hours
 - if dexamethasone level is low, the test will be repeated with a higher dose of dexamethasone; 3mg overnight test with a cortisol suppression threshold set at 3 µg/dL
 - cortisol at 08:00 hours
 - plasma dexamethasone level at 08:00 hours

2.2.4.7 Serum fractionated plasma normetanephrine and metanephrine

2.2.4.8 24-hour urinary epinephrine, dopamine, norepinephrine, fractionated normetanephrines, fractionated metanephrines

2.3 REGISTRATION PROCEDURES

Authorized staff must register an eligible candidate with NCI Central Registration Office (CRO) within 24 hours of signing consent. A registration Eligibility Checklist from the web site (<http://home.ccr.cancer.gov/intra/eligibility/welcome.htm>) must be completed and sent via encrypted email to: NCI Central Registration Office (HOIS) <[contact]>. Verification of Registration will be forwarded electronically via e-mail to the research team. A recorder is available during non-working hours.

2.4 RANDOMIZATION (OR STRATIFICATION) PROCEDURES

Patients with subclinical hypercortisolism will be randomized to adrenalectomy or observation as defined above and followed for 6 months. At the end of 6 months, the patients who were in the observation-only arm will all be offered an adrenalectomy. Patients with subclinical hypercortisolism tend to have high prevalence of metabolic consequences, specifically hypertension, diabetes, osteoporosis, hypercholesterolemia, and/or obesity. The patients will be randomized by the CRO.

To be conservative, the primary goal of this study will be to determine if the use of adrenalectomy is associated with 35% improvement vs. 5% improvement over 6 months without surgery as defined for any one or more of the following associated metabolic complications: hypertension, diabetes, osteoporosis, hypercholesterolemia, and/or obesity. With 31 patients per arm (62 total), there would be 80% power to detect a difference of this magnitude using a 0.05 significance level two-tailed Fisher's exact test.

Abbreviated Title: Subclinical Hypercortisolism**Version Date: 12/19/2016**

The following definitions will be used to determine if a given metabolic complication shows sufficient improvement in order to be considered as a component of a successful outcome:

Hypertension: normalization and/or improvement in blood pressure as assessed by reduction in pharmacotherapy and/or normalization of blood pressure (systolic pressure ≤ 140 and diastolic pressure ≤ 90) from baseline.

Diabetes: normalization and/or improvement in diabetes as assessed by normalization (A1C $< 6.5\%$), and/or reduction and/or discontinuation of pharmacotherapy.

Osteoporosis: an increase in the level of bone formation markers greater than the least significant change, which is calculated by multiplying the “precision error” of the specific biomarker by 2.77 (95% confidence interval) as per the National Osteoporosis Foundation (NOF) Clinician’s Guide to Prevention and Treatment of Osteoporosis 2013 ([Appendix D](#)).

Hypercholesterolemia: improvement in cholesterol as assessed by a reduction or elimination of pharmacotherapy and/or reduction in LDL levels to the optimal risk stratified goal as defined by ATP III guidelines ([Appendix E](#)).

Obesity: improvement in obesity as defined by a ten percent reduction in fasting morning weight compared to baseline.

2.5 BASELINE EVALUATION

Patients will undergo the following evaluations which may be performed within 4 weeks after enrollment, prior to randomization.

2.5.1 Detailed History and Physical Examination

H & P will include vital signs, BMI, weight, waist circumference, ECOG status, demographic information and family history.

2.5.2 Quality of Life Questionnaire (see [Appendix A](#))

2.5.3 Radiology and Nuclear Medicine Tests

2.5.3.1 Adrenal protocol CT scan with and without intravenous contrast.

2.5.3.2 FDG PET/CT scan

2.5.3.3 DEXA scan with body composition.

2.5.3.4 Bilateral lower extremity duplex

2.5.3.5 Vertebral X-rays as assessed by vertebral morphometry and body composition

2.5.3.6 Ultrasound of the skin at three locations: the abdomen, volar aspect of the forearm, and the thigh (as described by Schou et. al. (34))

2.5.4 Specialty Consults as Required by Patient’s Medical History and Presentation

2.5.5 Laboratory evaluation

2.5.5.1 CBC with differential

2.5.5.2 Chemistry Panel [Sodium (Na), Potassium (K), Chloride (Cl), Total CO₂ (bicarbonate), Creatinine, Glucose, Urea Nitrogen (BUN), Albumin, Calcium total, Magnesium total

Abbreviated Title: Subclinical Hypercortisolism**Version Date: 12/19/2016**

(Mg), Inorganic Phosphorous, Alkaline Phosphatase, ALT/GPT, AST/GOT, Total Bilirubin, Direct Bilirubin, LD, Total Protein, Total CK, Uric Acid]

2.5.5.3 PT/PTT

2.5.6 Biochemical testing

2.5.6.1 Fasting morning upright serum renin and plasma aldosterone levels

2.5.6.2 24 hour urinary free cortisol level

2.5.6.3 Midnight serum and salivary cortisol level

2.5.6.4 Baseline serum cortisol at 08:00 and 16:00 hours

2.5.6.5 Morning plasma ACTH at 08:00

2.5.6.6 Low dose dexamethasone suppression test

1mg overnight test with a cortisol suppression threshold set at 3 µg/dL

- cortisol at 08:00 hours
- plasma dexamethasone level at 08:00 hours
 - if dexamethasone level is low, the test will be repeated with a higher dose of dexamethasone; 3mg overnight test with a cortisol suppression threshold set at 3 µg/dL
 - cortisol at 08:00 hours
 - plasma dexamethasone level at 08:00 hours

2.5.7 Other Laboratory Evaluations

2.5.7.1 Serum fractionated plasma normetanephrine and metanephrine

2.5.7.2 24-hour urinary epinephrine, dopamine, norepinephrine, fractionated normetanephrines, fractionated metanephrines

2.5.7.3 Dehydroepiandrosterone sulfate

2.5.7.4 Urinary 17 ketosteroids

2.5.7.5 Testosterone (both males and females)

2.5.7.6 24 hour urinary calcium, phosphorous, and amino acid random urine.

2.5.7.7 25-OH Vitamin D level

2.5.7.8 Parathyroid hormone (PTH)

2.5.7.9 Thyroid stimulating hormone (TSH)

2.5.7.10 Fasting glucose, Hgb A1C

2.5.7.11 C-reactive protein (CRP)

[figure not shown]
2.5.7.12 Fasting Triglyceride, total cholesterol, LDL, HDL levels

3 STUDY IMPLEMENTATION

3.1 STUDY DESIGN

This is a prospective randomized study of individuals with an adrenal mass less than or equal to 5 cm with biochemically confirmed hypercortisolism (2 out of 3: DST >3 mmol/l, elevated urine free cortisol, and/or morning ACTH <2.2 pmol/l) without overt clinical signs and/or symptoms (facial plethora, easy bruising, violaceous striae, and/or proximal muscle weakness) of excess cortisol. Individuals will undergo a clinical work up for an adrenal mass including laboratory and radiological studies (see below). Patients diagnosed with subclinical hypercortisolism and an adrenal mass less than 5 cm will be randomly assigned to either the non-operative or operative arm of the study. In patients found to have bilateral adrenal masses, the larger of the two masses will be treated as the adrenal lesion responsible for subclinical hypercortisolism. These patients with bilateral adrenal masses will be randomly assigned to either the non-operative or operative arm of the study. The responsible lesion will be adrenal mass that will be removed with a unilateral adrenalectomy or monitored. For patients in the non-operative or medical treatment-only arm, baseline evaluation will be undertaken, as well as follow up and re-evaluation every 3 months for 6 months, after which they will crossover to the operative arm and undergo an adrenalectomy. If a patient develops overt signs and symptoms of cortisol excess during the 6 months of observation, the tumor grows after enrollment during the 6 months of observation or 6 months have elapsed, the patient will cross over to the operative arm, and undergo an adrenalectomy. Worsening of metabolic complications will not be an indication for crossover. Patients after crossing over to the operative arm will have follow up every 3, 6, 9, and 12 months for the first year, six month follow up thereafter for the second year, and yearly follow up thereafter for three years. For a patient in the operative arm, the patient will undergo baseline evaluation, adrenalectomy, and follow up every 3, 6, 9, and 12 months for the first year, six month follow up thereafter for the second year, and yearly follow up thereafter for three years. At each follow-up visit, the patient will undergo repeat radiological and laboratory evaluation (see [Table 1](#)). Uniformity of medical management will be ensured by coordinating with primary care physicians, endocrinologists and the utilization of national guidelines in treating the metabolic manifestations and consequences of subclinical hypercortisolism.

Table 1

Abbreviated Title: Subclinical Hypercortisolism**Version Date: 12/19/2016****3.2 QUESTIONNAIRES**

The questionnaires to be utilized include the generic SF-36 and the Cushing specific quality of life questionnaire (26). The questionnaires will assess the patient's quality of life preoperatively and postoperatively. The questionnaires will take approximately ten minutes to complete. The SF-36 form will be given first, and the Cushing's specific quality of life questionnaire will follow. The topics will address general health and wellbeing. After the questionnaires are collected and entered into a computer database, the data will be shredded.

*Abbreviated Title: Subclinical Hypercortisolism**Version Date: 12/19/2016***3.3 STUDY CALENDAR****3.3.1 Operative Arm**

Baseline and Follow-up Testing for Operative Arm					
Test	Baseline evaluation (MO)	3 monthly evaluation (M3)	3 monthly evaluation (M6, M9)	6 monthly evaluation (M12, M18)	12 monthly evaluation (M24, M36, M48, M60)
QoL Questionnaire	x	x		x	
CT adrenal	x				
FDG PET/CT scan	x				
DEXA	x			x	x
Duplex	x	x			
Vertebral (X-rays) morphometry and body composition	x	x	x		
Skin ultrasound	x	x	x	x	x
CBC	x	x	x	x	x
Chemistries	x	x	x	x	x
PT/PTT/INR	x				
Renin/PAC	x				
24 hour urine free cortisol	x	x			
midnight serum/salivary cortisol	x	x			
baseline serum cortisol	x	x			
DST	x	x			
plasma ACTH	x	x			
serum fractionated plasma normetanephrines and metanephrines	x				
24-hour urinary epinephrine, dopamine, norepinephrine, and fractionated normetanephrines and metanephrines	x				
DHEA	x	x	x	x	
Urinary 17 ketosteroids	x	x	x	x	x
testosterone	x	x			
24 hour urinary calcium, phosphorous,	x	x	x	x	x

*Abbreviated Title: Subclinical Hypercortisolism**Version Date: 12/19/2016*

Baseline and Follow-up Testing for Operative Arm					
Test	Baseline evaluation (MO)	3 monthly evaluation (M3)	3 monthly evaluation (M6, M9)	6 monthly evaluation (M12, M18)	12 monthly evaluation (M24, M36, M48, M60)
amino acid random urine					
25-OH Vitamin D Level	x	x	x	x	x
PTH	x	x			
fasting glucose	x	x	x	x	x
A ₁ C	x	x	x	x	x
Triglyceride, total LDL, HDL levels	x	x	x	x	x
NIH Advanced Directives Form¹	x				

¹ As indicated in section 8.3, all subjects will be offered the opportunity to complete an NIH advanced directives form. This should be done preferably at baseline but can be done at any time during the study as long as the capacity to do so is retained. The completion of the form is strongly recommended, but is not required.

3.3.2 Non-Operative Arm

Baseline and Follow-up Testing for Non-Operative Arm						
Test	Baseline evaluation (MO)	Preop 3 monthly evaluation (M3, M6)	3 monthly evaluation (M9)	3 monthly evaluation (M12, M15)	6 monthly evaluation (M18, M24)	12 monthly evaluation (M30, M42, M54, M66)
QoL Questionnaire	x	x	x		x	
CT adrenal	x	x				
FDG PET/CT scan	x					
DEXA	x				x	x
Duplex	x	x	x			
Vertebral (X-rays) morphometry and body composition	x		x	x		
Skin ultrasound	x	x	x	x	x	x
CBC	x	x	x	x	x	x
Chemistries	x	x	x	x	x	x
PT/PTT/INR	x					
Renin/PAC	x					

*Abbreviated Title: Subclinical Hypercortisolism**Version Date: 12/19/2016*

Baseline and Follow-up Testing for Non-Operative Arm						
Test	Baseline evaluation (MO)	Preop 3 monthly evaluation (M3, M6)	3 monthly evaluation (M9)	3 monthly evaluation (M12, M15)	6 monthly evaluation (M18, M24)	12 monthly evaluation (M30, M42, M54, M66)
24 hour urine free cortisol	x	x	x			
midnight serum/salivary cortisol	x	x	x			
baseline serum cortisol	x	x	x			
DST	x	x	x			
plasma ACTH	x	x	x			
serum fractionated plasma normetanephrines and metanephrines	x	x				
24-hour urinary epinephrine, dopamine, norepinephrine, and fractionated normetanephrines and metanephrines	x	x				
DHEA	x	x	x	x	x	
Urinary 17 ketosteroids	x	x	x	x	x	x
testosterone	x	x	x			
24 hour urinary calcium, phosphorous, amino acid random urine	x	x	x	x	x	x
25-OH Vitamin D Level	x	x	x	x	x	x
PTH	x	x	x			
fasting glucose	x	x	x	x	x	x
A ₁ C	x	x	x	x	x	x
Triglyceride, total LDL, HDL levels	x	x	x	x	x	x

Abbreviated Title: Subclinical Hypercortisolism

Version Date: 12/19/2016

Baseline and Follow-up Testing for Non-Operative Arm						
Test	Baseline evaluation (MO)	Preop 3 monthly evaluation (M3, M6)	3 monthly evaluation (M9)	3 monthly evaluation (M12, M15)	6 monthly evaluation (M18, M24)	12 monthly evaluation (M30, M42, M54, M66)
NIH Advanced Directives Form¹						

¹ As indicated in section 10.3, all subjects will be offered the opportunity to complete an NIH advanced directives form. This should be done preferably at baseline but can be done at any time during the study as long as the capacity to do so is retained. The completion of the form is strongly recommended, but is not required.

3.4 SURGICAL GUIDELINES

After randomization, patients in the surgery arm will undergo an adrenalectomy as per standard of care.

3.5 CRITERIA FOR REMOVAL FROM PROTOCOL THERAPY AND OFF STUDY CRITERIA

3.5.1 Criteria for removal from protocol therapy

- Patient request to be withdrawn
- PI discretion, if the PI feels it is not in the best interest of the patient to remain on study
- Completion of protocol therapy
- Positive pregnancy test

3.5.2 Off-Study Criteria

Patients will be removed from the study if any of the following criteria are met:

- Patient requests withdrawal from the study
- Patient is consistently non-compliant with the follow-up appointments
- Completion of the protocol specified follow up period
- PI discretion
- Death

3.5.3 Off-Study Procedure

Authorized staff must notify Central Registration Office (CRO) when a subject is taken off-study. An off-study form from the web site (<http://home.ccr.cancer.gov/intra/eligibility/welcome.htm>) main page must be completed and sent via encrypted email to: NCI Central Registration Office (HOIS) <[contact]>.

Abbreviated Title: Subclinical Hypercortisolism

Version Date: 12/19/2016

4 BIOSPECIMEN COLLECTION

4.1 CORRELATIVE STUDIES FOR RESEARCH

Patients will be co-enrolled on protocol 09-C-0242. Biospecimen will be collected as specified in protocol 09-C-0242.

4.2 SAMPLE STORAGE, TRACKING AND DISPOSITION

Tissue will be snap frozen in liquid nitrogen and transported to the Endocrine Oncology Lab by calling [contact]. Samples will be labeled with the date and time of acquisition, the type of tissue and patient study ID. Upon receipt in the lab, samples will be bar coded and logged in to the tissue database, LabMatrix. Tissue will be stored in -20 °C or -80 °C freezers. All freezers are monitored and are on separate emergency generator lines.

Serum and urine samples for correlative studies may also be obtained and will be stored and tracked in the same manner as tissue samples.

At the completion of the protocol, the investigator will dispose of all specimens in accordance with the environmental protection laws, regulations and guidelines of the Federal Government and the State of Maryland. {Note, all patients undergoing surgery for endocrine diseases that consent to have their tissue used for research will be enrolled on this trial and thus the trial will remain ongoing as long as identified samples are being used in the conduct of this research. It is anticipated that this protocol will remain open for at least the next 6 years}

Any loss or unintentional destruction of the samples will be reported to the IRB.

5 DATA COLLECTION AND EVALUATION

5.1 DATA COLLECTION

Data prior to and during the course of the patient's participation will be collected in order to monitor patient eligibility, and will include review of medical and family history records, completed questionnaires, non-invasive imaging and blood work. Data will be securely stored in the Labmatrix database.

The PI will be responsible for overseeing entry of data into an in-house password protected electronic system and ensuring data accuracy, consistency and timeliness. The principal investigator, associate investigators/research nurses and/or a contracted data manager will assist with the data management efforts. All data obtained during the conduct of the protocol will be kept in secure network drives or in approved alternative sites that comply with NIH security standards. Primary and final analyzed data will have identifiers so that research data can be attributed to an individual human subject participant.

End of study procedures: Data will be stored according to HHS, FDA, and NIH Intramural Records Retention Schedule regulations as applicable.

Loss or destruction of data: Should we become aware that a major breach in our plan to protect subject confidentiality and trial data has occurred, the IRB will be notified.

Abbreviated Title: Subclinical Hypercortisolism

Version Date: 12/19/2016

5.2 ROUTINE DATA COLLECTION

Following enrollment, all adverse events will be described in the source documents and be reviewed by the designated research nurse, and captured in C3D.

During the follow up period (more than 30 days following surgery), only those events that are serious, unexpected, and related to the treatment will be captured in C3D.

Exclusions to Routine Data Collection:

The following Adverse Events will be captured only in the source documents and will not be reported in C3D:

- Laboratory values that do not support the diagnosis of a reportable event
- All grade 1 events

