5.4 RESPONSE CRITERIA

For the purposes of this study, patients in the operative arm will be re-evaluated for response every 3 months from M0 to M12, every 6 months from M12 to M24, and then every 12 months thereafter through M60. Patients in the non-operative arm will be re-evaluated for response every 3 months from M0 to M18, every 6 months from M18 to M30, and then every 12 months thereafter through M66.

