6.1 DEFINITIONS

6.1.1 Adverse Event

An adverse event is defined as any reaction, side effect, or untoward event that occurs during the course of the clinical trial associated with the research in humans, whether or not the event is considered related to the treatment or clinically significant. For this study, AEs will include

events reported by the patient, as well as clinically significant abnormal findings on physical examination or laboratory evaluation. A new illness, symptom, sign or clinically significant laboratory abnormality or worsening of a pre-existing condition or abnormality is considered an AE.

All AEs, including clinically significant abnormal findings on laboratory evaluations, regardless of severity, will be followed until return to baseline or stabilization of event. Serious adverse events that occur more than 30 days after the last study procedure and have an attribution of at least possibly related to the agent/intervention should be recorded and reported as per section 6.2.

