6.2.2 NCI-IRB Requirements for PI Reporting at Continuing Review

The protocol PI will report to the NCI-IRB:

1. A summary of all protocol deviations in a tabular format to include the date the deviation occurred, a brief description of the deviation and any corrective action.
2. A summary of any instances of non-compliance
3. A tabular summary of the following adverse events:
 - All Grade 2 **unexpected** events that are possibly, probably or definitely related to the research;
 - All Grade 3 and 4 events that are possibly, probably or definitely related to the research;
 - All Grade 5 events regardless of attribution;
 - All Serious Events regardless of attribution.

Abbreviated Title: Subclinical Hypercortisolism

Version Date: 12/19/2016

NOTE: Grade 1 events are not required to be reported.

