6.3 DATA AND SAFETY MONITORING PLAN

6.3.1 Principal Investigator/Research Team

The clinical research team will meet on a regular basis when patients are being actively followed on the trial to discuss each patient.

All data will be collected in a timely manner and reviewed by the principal investigator or a lead associate investigator. Adverse events will be reported as required above. Any safety concerns, new information that might affect either the ethical and or scientific conduct of the trial, or protocol deviations will be immediately reported to the IRB using iRIS.

The principal investigator will review adverse event and response data on each patient to ensure safety and data accuracy. The principal investigator will personally conduct or supervise the investigation and provide appropriate delegation of responsibilities to other members of the research staff.

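### C3D adverse-event capture narrows 30 days after surgery, so within the randomised 6 months the narrow rule normally applies to the operative arm only

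*Combined protocol and SAP*

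**What the plan says.** Section 5.2 starts with a broad rule that is the same in both arms: "Following enrollment, all adverse events will be described in the source documents and be reviewed by the designated research nurse, and captured in C3D". Grade 1 events, and laboratory values that do not support a reportable event, stay in the source documents only. The section then sets a second rule by the date of surgery: "During the follow up period (more than 30 days following surgery), only those events that are serious, unexpected, and related to the treatment" are captured in C3D. All three conditions must hold.

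The date of surgery depends on the assigned arm. Sections 2.4 and 7 randomise patients to adrenalectomy or observation and follow them for 6 months. Section 3.4 places the operative arm's surgery after randomisation without giving a window, and section 7 describes it as immediate. The observation arm comes to surgery at 6 months. Section 3.1 allows this earlier only for overt signs and symptoms or tumour growth.

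Two other sections deal with late or reportable events. Section 6.1.1 asks for recording and reporting of "Serious adverse events that occur more than 30 days after the last study procedure and have an attribution of at least possibly related" to the intervention. Section 6.2.2 lists what goes to the IRB at continuing review, without a time limit, including "All Serious Events regardless of attribution" and "All Grade 3 and 4 events that are possibly, probably or definitely related to the research".

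**The concern.** A recording rule that starts at surgery is harmless in a cohort where every patient has surgery at time zero. Here one arm has surgery at the start of the 6-month comparison and the other at its end. The same event at the same time since randomisation can therefore be entered in C3D for one arm and left out for the other.

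Take a non-serious grade 2 worsening of a pre-existing condition at month 4. Section 6.1.1 counts it as an adverse event. It is entered for an observation patient who has not had surgery, but not for a patient operated on more than 30 days earlier. Section 8.5 names worsening of metabolic complications as a main risk of the observation arm, so this class of event matters to the balance of benefit and harm. At stake is the fairness of any harms table by arm that is drawn from C3D.

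**Working it through.** **Plan's own figures.** The plan gives no figure for adverse-event capture. Its design figure is 80% power with 31 patients per arm (35% v 5%, two-sided Fisher's exact test at 0.05). Full enumeration of the two binomial outcomes gives 80.9%, so that figure reproduces. It does not depend on adverse-event recording; only the 31 per arm is used below.

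**Inputs.** Comparison period: 6 months, taken as 183 days from randomisation (sections 2.4 and 7). Broad capture after surgery: 30 days (section 5.2). Delay from randomisation to surgery, s: not stated, so assumed. The baseline work-up does not add to s, because section 2.5 says: "Patients will undergo the following evaluations which may be performed within 4 weeks after enrollment, prior to randomization".

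**Formula.** Restricted days in the operative arm = 183 − s − 30.

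| Assumed delay s (days) | Restricted days | Share of 183 | Patient-days, 31 patients (of 31 × 183 = 5,673) |
|---|---|---|---|
| 0 | 153 | 84% | 4,743 |
| 28 | 125 | 68% | 3,875 |
| 56 | 97 | 53% | 3,007 |
| 90 | 63 | 34% | 1,953 |

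The share passes below one half between s = 61 (92 days, 50.3%) and s = 62 (91 days, 49.7%).

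**Observation arm.** 0 restricted days without early crossover. A patient who crossed over with surgery on day 91 (assumed) would have 183 − 91 − 30 = 62 restricted days.

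**Other clock.** Section 7 measures the operative arm's blood pressure 6 months after surgery. Counted that way, the restricted period is 183 − 30 = 153 days (84%) whatever the delay.

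**Which events drop out.** In the restricted period C3D omits non-serious events of grade 2 or higher, and serious events that are expected or unrelated. Section 6.2.2 still asks for all serious events, all grade 5 events, related grade 3 and 4 events, and unexpected related grade 2 events. What reaches neither is mainly non-serious events that are unrelated, or that are grade 2 and expected.

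The documents give no adverse-event rates by arm or over time, so no event counts or size of bias are estimated.

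**The case against.** The strongest reply is that no stated use of the data is harmed. Section 7 plans no between-arm comparison of adverse events. Section 5.2 keeps all events in source documents. Surgical complications within 30 days are fully captured. A1C, glucose and lipids are tested on schedule in both arms. Section 6.3.1 adds that "The principal investigator will review adverse event and response data on each patient to ensure safety and data accuracy". All of this stands, and it limits the point to tables built from C3D. It does not remove the point, because the arm difference follows from applying section 5.2 exactly as written.

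A reader might also infer that section 5.2 breaches section 6.2.2, because C3D would not hold every event that 6.2.2 lists. The documents do not support that. Section 5.2 governs database entry and 6.2.2 governs reporting to the IRB; nothing says that C3D must supply the 6.2.2 table, and source documents can. Nor should C3D be made to hold every such event. That would mean entry in both arms for years (M60 in the operative arm; in the other arm evaluations run "every 6 months from M18 to M30, and then every 12 months thereafter through M66") and would clash with keeping a restricted rule after month 6.

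A reader might think that 5.2 leaves a patient who never has surgery undefined. It does not: the narrow rule is never triggered and full capture continues.

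Finally, section 6 calls the protocol observational. That is a separate issue, the same in both arms, and it lends no support to this point.

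**Conclusion.** The point holds and is worth fixing because the remedy is cheap. As written, C3D capture within the 6-month comparison depends on the assigned arm. The operative arm is under the narrow rule for 53% to 84% of 183 days at assumed delays of 56 to 0 days, and the observation arm for none without early crossover. A C3D table by arm could show fewer non-serious events of grade 2 or higher, or fewer expected or unrelated serious events, after adrenalectomy partly because they were not entered.

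The tempting stronger reading is that the trial's main result is biased or that harms are lost. Neither follows. The primary endpoint rests on response evaluations set out in section 5.4, power is unchanged, and the events remain in source documents.

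The size rests on the assumed delay to surgery and on counting from randomisation; a longer delay shrinks it.

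There is also a minor wording point, the same in both arms. The late-event sentence in 6.1.1 requires at least possible relatedness and counts from a last study procedure that is not defined, while 6.2.2 takes serious events whatever their attribution and without a time limit.

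**What to change.** In section 5.2, keep full C3D capture in both arms, with the existing grade 1 and laboratory exclusions, until the later of:

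- (a) 6 months from randomisation, or the patient's 6-month evaluation if that is later; and
- (b) 30 days after the patient's own surgery.

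Apply the restricted rule only after that. Any by-arm adverse-event summary should use the common window in which both arms are under full capture.

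The 6-month evaluation needs naming because the operative arm's may be counted from surgery: at an assumed 56-day delay it falls near day 183 + 56 = 239.

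Separately, reconcile 6.1.1 and 6.2.2 on late serious events: define the last study procedure, and say whether relatedness and a time limit apply. C3D need not be the source of the 6.2.2 table.

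**Cost.** A protocol amendment, and C3D entry of events already in source documents for about 31 operative-arm patients. The extra period is 97 to 153 days each, about 3 to 5 months, at assumed delays of 56 to 0 days counted from randomisation, and 153 days if counted to 6 months after surgery. Any early crossover adds a little more. Sample size, visits and the primary analysis do not change. The documents do not allow the staffing effect to be judged.
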